Appendix to:

[name] et al

Sentinel lymph node detection in endometrial cancer. A consolidation study.

Table 1. Participating Sites and Site-Principal Investigators

Site	Site-PI	# patients enrolled
1. Department of Obstetrics and Gynecology, Skåne University Hospital and Lund University, Lund, Sweden	[name]	XX
2. To be decided		

Supplementary appendix

[name] et al

Sentinel lymph node detection in endometrial cancer. A consolidation study.

Coordinating Center: Department of Obstetrics and Gynecology, Skåne, Lund University Hospital and Lund University, Lund Sweden.

Lead Principal Investigator: [name] MD PhD Associate Professor
Department of obstetrics and Gynecology, Division of Gynecologic Oncology
Skåne University Hospital Lund
[name]
(ph) [name]
(fax) [name]
Email: [contact]

Local Principal Investigator:

Study Coordinator: [name] MD
Department of obstetrics and Gynecology, Division of Gynecologic Oncology
Skåne University Hospital Lund
[name]
(ph)[name]
(fax) [name]
Email: [contact]

[figure not shown]
Study Statistician:

[name]. Faculty of Engineering, Lund University.

Overview study plan.

Consecutive eligible high and low risk endometrial cancer planned for robotic surgery, clinically with the primary tumor confined to the uterus (uterine stage I-II).

High risk defined as at least either of deep ($\geq 50\%$) myometrial invasion, cervical stromal invasion, endometrioid cancer FIGO grade 3, or a non-endometrioid histology. FIGO grade 1-2 endometrioid cancer with no myometrial invasion are defined as low risk.

Define/ plan also as of below:

1. **FIGO grade 1-2 endometrioid cancers regardless of myometrial invasion.**

SLN UPP and parametria. Ipsilateral reinjection only if non-display of UPP. No frozen section of SLN unless macro. Removal of nodes at typical positions for SLN (External, obturator, common) in case of non-display of UPP uni or bilaterally

2. **FIGO grade 3, undifferentiated or non-endometrioid cancers.**

SLN UPP, parametria and LPP. Ipsilateral reinjection if non-display of UPP. Removal of nodes at typical positions for SLN (External, obturator, common) in case of non-display of UPP uni or bilaterally. Full uni-bilateral presacral LND if non-display of LPP. No frozen section of SLN unless macro.

3. **Any endometrial cancer with cancer suspect pelvic or paraaortic nodes**

according to RECIST criteria (≥ 16 mm short axis). SLN detection/reinjection as for 2 above. Frozen section of SLN. Patient upfront surgery planned for pelvic and paraaortic lymphadenectomy. Pelvic and paraaortic LND if frozen section verifies cancer.

UPP- Upper paracervical pathway

LPP- Lower paracervical pathway

Parametria= upper lymphovascular paracervical tissue medial of the umbilical artery, dorsal of the supravesical artery, lateral of the medial broad ligament and ventral of the ureter.

.

Pelvic SLN identification with near infrared technique for identification of Indocyanine green (ICG) in lymphatics and lymph nodes. Ipsilateral cervical reinjection of ICG as of above 1-3. Registration of SLN- associated intraoperative adverse events.

Complete pelvic lymphadenectomy and a Querleu-Morrow Type A to C1 hysterectomy and bilateral adnexectomy. Registration of associated intraoperative adverse events.

SLN's for ultrasectioning and immunohistochemistry. Any remaining nodes for standard pathological bisectioning and staining with hematoxylin/Eosine.

Restaging surgery in case of a positive SLN. US and IHC of restaged nodes if compatible with department of pathology.

Registration of postoperative adverse events until 30 days after surgery

At one year postop or at symptoms. Postoperative bilateral measurement of leg volume.
Preoperative QOL lymphatic system and symptom score.

Table of contents

1.0	OBJECTIVES	
2.0	BACKGROUND	
3.0	PATIENT AND SURGEON ELIGIBILITY	
4.0	STUDY MODALITIES	

5.0	TREATMENT PLAN	
6.0	TREATMENT MODIFICATIONS	
7.0	STUDY CRITERIA	
8.0	EVALUATION CRITERIA	
9.0	DURATION OF STUDY	
10.0	STUDY MONITORING AND REPORTING PROCEDURES	
11.0	STATISTICAL CONSIDERATIONS	
12.0	BIBLIOGRAPHY	

1. OBJECTIVES

To estimate the efficacy of a pelvic sentinel lymph node (SLN) concept for diagnose of pelvic nodal metastases in patients with low and- high risk endometrial cancer using a cervical injection of Indocyanine Green (ICG) as tracer and robot assisted near infrared (NIR) imaging using an anatomically based surgical algorithm and definition of sentinel lymph nodes. The observed percentage of metastatic sentinel nodes will be evaluated from a non-inferiority perspective based on an assumed percentage of pelvic nodal metastases estimated from final detailed histological data (myometrial invasion, cervical stromal invasion, histological type and grade)

To estimate the proportion of low- and high risk endometrial cancer patients suitable for the SLN concept in conjunction with robotic surgery

To estimate time for the SLN procedure and intraoperative complications associated with detection of SLN as such (study intervention) and postoperative adverse events until 30 days as well as objective measurement of leg volume and lymphedema symptoms by the use of a validated questionnaire up and until two years after surgery.

To estimate health economy aspects of the SLN concept.

To estimate complications associated with ICG as tracer

2. BACKGROUND

The surgical approach for endometrial cancer staging has changed from conventional laparotomy to a more minimally invasive technique with proven advantages in terms of less perioperative morbidity. In endometrial cancer, nodal involvement is a strong prognostic factor and also determines adjuvant treatment. Therefore information on nodal metastases is important and in many countries a full pelvic and paraaortic lymphadenectomy is recommended despite an increased risk for lymphatic complications in form of lymphedema, lymphocysts and in rare cases lymphatic ascites. The concept of identifying nodal metastases by detection of sentinel lymph nodes as a marker of nodal metastatic disease or not therefore is appealing.

Recent data from the department of Obstetrics and Gynecology in Lund shows that robot assisted surgery with detection of sentinel lymph nodes with the use of ICG is feasible 84% of unselected endometrial cancer patients selected for primary surgery using the inclusion criteria in this study. Recent data also shows a 94% bilateral detection rate of sentinel nodes (technical success rate) and a 98% sensitivity for the SLN-ICG concept for detecting pelvic nodal metastases.

By the use of Indocyanine green, a fluorescent tracer, we have also previously demonstrated two bilateral separate pelvic pathways, the upper paracervical pathway (UPP) running along the upper lymphovascular parametrium usually to external iliac and/ or obturator nodes and the further lateral to the common iliac artery to paraaortic nodes and the lower paracervical pathway (LPP) running via the sacrouterine ligament to nodes medial of the internal iliac artery and/ or presacral nodes then further medial to the common iliac artery to paraaortic nodes. Hence there are two bilateral pelvic pathways draining further to the paraaortic region below as well as above the inferior mesenteric artery. Therefore we believe that lower paraaortic SLN can only be defined in the absence of pelvic SLN along the pathways but with clear filling of pelvic lymphatic channels up to the aorta. In previous studies and pilot studies at our institution we have never observed this situation.

Alternatively, lymph nodes cranial of the inferior mesenteric artery but caudal of the left renal vein (infrarenal, supramesenteric nodes) theoretically may be dyed via the infundibulopelvic ligament and may then be considered as true paraaortic SLN but only in the absence of dyed node more caudally. Neither this situation has been observed after a cervical injection of tracer rarely filling the infundibulopelvic ligament. Moreover, attempts

to find paraaortic SLN would be a step away from decreasing surgery in endometrial cancer. Although detection of pelvic SLN may miss paraaortic skip metastases we hypothesize that ultrasectioning of SLN and including a presacral dissection of SLN may decrease the incidence of true paraaortic skip metastases.

Surgical competence and experience is necessary to achieve a high technical success rate and a low false negative rate for SLN.

This study aims to evaluate the pelvic sentinel node concept based on a defined surgical algorithm and with a clear definition of SLN based on described uterine lymphatic anatomy. The study setting includes only high volume accredited surgeons enabling an evaluation of the true potential of the pelvic SLN concept in endometrial cancer.

This study aims to include consecutive low and high endometrial cancer patients fulfilling criteria to ensure the results are representative for the endometrial cancer population.

3. PATIENT ELIGIBILITY

Inclusion Criteria

- Women of age 18 years and older at the time of informed consent.
- Women with a pathologically proven endometrial carcinoma of any histologic subtype or grade, clinically stage I-II planned for primary surgery
- A uterine size allowing minimally invasive surgery
- Women must be able to understand and sign an informed consent in Swedish language.
- Absence of any exclusion criteria

Exclusion Criteria

- Non consenting patients
- Ongoing pregnancy
- Inability to understand written and/or oral study information
- WHO performance status or conditions contraindicating adjuvant oncological treatment (WHO III or more with no BMI limit)
- Previous lower limb lymphedema (only for the lymphedema part of study)
- Evidence of locally advanced disease or intraabdominal/distant metastases at preoperative CT, MRI or ultrasonography.
- Surgical contraindication to a laparoscopic approach or lymphadenectomy at surgeons discretion.
- Anesthesiologic contraindication to a laparoscopic approach at the anesthetist's discretion
- Allergy to Iodine
- Patients with a known liver disease
- Patients with a bleeding disorder or mandatory antithrombotic treatment.

WHO Performance status

Grade	Explanation of activity
0	Fully active, able to carry on all pre-disease performance without restriction
1	Restricted in physically strenuous activity but ambulatory and able to carry out work of a light or sedentary nature, e.g., light house work, office work
2	Ambulatory and capable of all selfcare but unable to carry out any work activities. Up and about more than 50% of waking hours
3	Capable of only limited selfcare, confined to bed or chair more than 50% of waking hours
4	Completely disabled. Cannot carry on any selfcare. Totally confined to bed or chair
5	Dead

Surgeon eligibility

All included surgeons outside the primary investigating center must have had a case observation at the primary investigating center followed by a an approved site visit by the principal investigating surgeon at their home center ensuring adherence to protocol. All included surgeons at the primary investigating center were approved by the principal investigating surgeon.

All included surgeons must have a previous experience of at least 100 robot-assisted procedures.

In case of additional centres later including patients: The departments of pathology shall be coordinated in terms of principles for ultra sectioning and immunohistochemistry of SLN and management on non-sentinel lymph nodes.

4.0/5.0 STUDY MODALITIES/ TREATMENT

Surgical Procedures

All patients; plan for QM B2 or C1 hysterectomy stage II), adnexectomy. Omentectomy in non-endometrioid or undifferentiated cancers

Define/ plan also as of below:

1. FIGO grade 1-2 endometrioid cancers regardless of myometrial invasion.

SLN UPP and parametria. Ipsilateral reinjection only if non-display of UPP. No frozen section of SLN unless macro. Removal of nodes at typical positions for SLN (External, obturator, common) in case of non-display of UPP uni or bilaterally

2. FIGO grade 3, undifferentiated or non-endometrioid cancers.

SLN UPP, parametria and LPP. Ipsilateral reinjection if non-display of UPP. Removal of nodes at typical positions for SLN (External, obturator, common) in case of non-display of UPP uni or bilaterally. Full uni-bilateral presacral LND if non-display of LPP. No frozen section of SLN unless macro.

3. Any endometrial cancer with cancer suspect pelvic or paraaortic nodes

according to RECIST criteria (≥ 16 mm short axis). SLN detection/reinjection as for 2 above. Frozen section of SLN. Patient upfront surgery planned for pelvic and paraaortic lymphadenectomy. Pelvic and paraaortic LND if frozen section verifies cancer.

[figure not shown]
UPP- Upper paracervical pathway

LPP- Lower paracervical pathway

Parametria= upper lymphovascular paracervical tissue medial of the umbilical artery, dorsal of the supravesical artery, lateral of the medial broad ligament and ventral of the ureter.

Typical positions of SLN for definition of “SLN-anatomy”

Positions of SLN in uterine cancer following a cervical injection of ICG

Drug Information:

Indocyanine Green solution (ICG) 2.5mg/mL.

Description: ICG (Pulsion medical system, PICG0025SE, Feldkirchen Germany) is a sterile, lyophilized green powder containing 25 mg of Indocyanine green with no more than 5% sodium iodide.

The ICG solution is prepared immediately before surgery and intended for single patient use. For preparation, 10mL of sterile water is injected directly into the lyophilized ICG in its glass vial. Invert the vial multiple times to ensure thorough mixing. Draw up 0,25 mL in six 1 mL syringes from the vial with ICG solution (2,5mg/mL) for the cervical injection. A 0.6x38mm 23Gx1 1/2 needle. The content of four of the syringes are used for the initial injection and in case of non-display of any pathway one or two of the other are used for an ipsilateral re-injection.

The ICG solution is stored at room temperature. The solution is active for 6 hours, and should be discarded after that period of time.

Manufacturer: Pulsion medical system, Feldkirchen Germany

Availability: ICG will be provided by the manufacturer to each site.

Adverse Effects if ICG: All adverse effects are allergic in nature and occur in <1% of patients. Anaphylactic or urticarial reactions have been reported in patients with or without a history of allergy to iodides. If such reactions occur, treatment with the appropriate agents (e.g. adrenalin, antihistamines, corticosteroids) should be initiated.

Contraindications: Known hypersensitivity to iodine containing compounds. Known liver failure. Radioactive iodine uptake studies should not be performed for at least 1 week following the use of ICG.

Please refer to the current ICG package insert for complete prescribing information

Injection of Indocyanine Green (ICG)

- The ICG is prepared by thorough mixing of 10mL of sterile water with the lyophilized ICG in its vial creating a 2.5mg/mL concentration. The lot number, expiration date and dose injected (mg) will be recorded.
- Six separate sterile 1mL syringes is prepared with 0.25 mL ICG solution (0.625 mg ICG) in each syringe is prepared.
- A 0.6x38 mm 23G needle is attached to each syringe for the injection. A separate back table is used for the syringes.
- The ICG injection will be performed immediately before placement of surgical port and docking the robot.
- Half the ICG volume in each syringe is injected submucosally and half the volume 3 cm into the cervical stroma at 2-4-8-and 10 O'clock respectively to a total dose of 2.5mg ICG and a total volume of 1 mL. Time for injection is recorded.
- After injection of dye, a fornix presenter without an intracervical device is placed
- A second ipsilateral injection of 0,25mL ICG is performed in case of non-display of either of the upper (UPP) or lower (LPP) paracervical pathways after a minimum of 10 minutes observation time after ICG injection. The injection is done at 3 and 9 O'clock respectively, half the volume submucosally and half the volume 3 cm into the cervix.
- Display of the separate lymphatic pathways (UPP, LPP and IPP will be recorded after the first and if performed after the second injection).

Sentinel Node Identification

The bilateral technical success rate of SLN identification is important to determine if this technique can be transferred to clinical practice. A clear anatomically definition of what is a SLN and a strict surgical algorithm as described in this study is important. Based on recent results from our institution on cervical and endometrial cancer we expect that the bilateral pelvic SLN identification (defined as at least one SLN per hemipelvis) will be 94%. A lower than expected detection rate will not be an incentive for premature stop of accrual. Importantly, accreditation of surgeons will be performed as described and is likely important to achieve a similar success rate as in previous studies.

The sentinel nodes are defined as the juxtauterine ICG positive node with an afferent ICG positive lymphatics in each of the UPP and LPP respectively on each pelvic side with the potential of parallel lymphatics in the UPP to the external and obturator areas. These SLN are defined as **SLN type 1**.

In case of a ICG positive lymph vessel where no nodes are ICG positive in that pathway, the node where the ICG positive lymphatic channel ends is defined as **SLN type 2**.

Nodes macroscopically suspect of metastatic disease will be defined as **SLN Macro** regardless of ICG uptake but with information on ICG positivity or not.

In case of no defined SLN 1-2 macro along the UPP and no **SLN macro** (low and high risk EC) nodes at typical positions shall be removed and regarded as **SLN-anatomy** and treated as SLN by the department of pathology. Likewise all endometrial cancers of FIGO grad III, undifferentiated or of non-endometrioid histology shall have a full presacral dissection in case of non-display. Those node shall be treated as SLN by the department of pathology.

Importantly, to secure accuracy, the positions and types of SLN will be marked on an anatomical chart, recorded on a list with anatomical locations and placed in pre-labeled jars with corresponding anatomical positions and numbers. This list is used by the department of pathology for reporting the results to minimize the risk of errors in location of nodes and which nodes are SLN's and non-SLN's. A copy of the list is kept in the patients study file.

Nodes defined as SLN will have red labels on the jars, other nodes will have black labels.

SLN's will be sent for final histological evaluation including ultrasectioning and immunohistochemistry as described. SLN's will not be sent for frozen section unless clinically motivated.

[figure not shown]
The display of ICG along the UPP shall be evaluated a minimum 10 minutes after the injection of ICG, first transperitoneally, and if not seen, after opening of the retroperitoneal avascular planes. An ipsilateral reinjection shall be performed in case of non-display of the UPP in both low risk (LREC) and high risk (HREC) endometrial cancers. A non-display of the LPP shall **not** motivate reinjection but in HREC a full presacral lymphadenectomy (LND). No presacral dissection shall be performed in LREC.

In case of non-display of the UPP despite reinjection a full lymphadenectomy in the external iliac and obturator areas shall be performed in HREC whereas in LREC LND a selective LND shall be performed including all macroscopically enlarged nodes and lymph nodes proximal in the obturator fossa and external iliac nodes in the bifurcation / between the external and internal iliac artery (typical positions of SLN's along the UPP).

To minimize disturbance by leaking ICG identification and removal of SLN's starts cranially, presacrally (along the LPP, HREC only) and continues at the pelvic side walls along the UPP. In both HREC and LREC and after removal of SLN's the upper lymphovascular parametrial tissue is removed separately (defined as the tissue along the uterine artery, medial to the obliterated umbilical artery and caudal of the supravesical artery) as it may contain lymph nodes that may not be separated from the green lymphovascular tissue and hence be the juxtauterine lymph node.

Anatomic boundaries of lymph node compartments in the female pelvis				
Lymph node compartment	Proximal limit	Lateral limit	Distal limit	Medial limit
External iliac area	Bifurcation of external and internal iliac artery	Genitofemoral nerve	Cloquet's lymph node	External iliac vein
Obturator fossa	Internal iliac vein	Ileopsoas muscle	Os pubis, obturator nerve	Obliterated umbilical artery
Common iliac	Aortic bifurcation	Genitofemoral nerve	Bifurcation of external and internal iliac artery	Common iliac artery
Presacral	Aortic bifurcation	Common iliac artery	Lower promontory	Hypogastric nerve (as distinction between right and left)

Anatomic description of lymphatic pathways draining the uterus

The upper paracervical pathway (UPP) follows the uterine artery to the pelvic side wall draining primarily to the external iliac and obturator nodal compartments, then running lateral to the common iliac artery further to the paraaortic area.

The lower paracervical pathway (LPP) follows the ventral rim of the sacrouterine ligament, primarily to internal iliac and presacral nodes, then running medial of the common iliac artery further to the paraaortic area.

The infundibulopelvic ligament pathway (IPP) runs via the Ip-ligament further to the supramesenteric paraaortic area.

For the pelvic SLN concept, ideally one SLN should be identified per LPP and UPP per pelvic side wall.

Anatomic plan for localization of sentinel lymph nodes

Injection site of ICG cervix

[figure not shown]
Reinjection cervix: yes no

Display after first injection

Display after second injection

	UPP	LPP	IP-ligament
Right			
Left			

	UPP	LPP	IP-ligament
Right			
Left			

Mark position and type of SLN on anatomical chart with number corresponding to position and number at list and on separate jars for each SLN.

O = ICG positive juxtauterine Sentinel node (**SLN1**)

= ICG neg juxtauterine lymph node with afferent lymphatic vessel (**SLN 2**)

X = Tumor suspect lymph nodes regardless of mapping (**SLN makro**)

List of nodal specimens (swedish) Endometrial cancer pat-id date

Om preparat saknas från station stryks raden i listan. Burknumrering behålls för övriga prep.

KK Burk nr	Körtelposition	Patal burk nr	Dosa nr	Antal bitar	Mikro Antal körtlar	Varav med metast
1	Uterus, höger ovarium & tuba, vänster ovarium & tuba					
2	Lgl Iliaca Externa höger ICG NEG					
3	Lgl Iliaca Externa höger ICG POS					
4	Lgl Obturatorius höger ICG NEG					
5	Lgl Obturatorius höger ICG POS					
6	Lgl Iliaca Communis höger ICG NEG					
7	Lgl Iliaca Communis höger ICG POS					
8	Lgl Presacral höger ICG NEG					
9	Lgl Presacral höger ICG POS					
10	Lgl Iliaca Externa vänster ICG NEG					
11	Lgl Iliaca Externa vänster ICG POS					
12	Lgl Obturatorius vänster ICG NEG					
13	Lgl Obturatorius vänster ICG POS					
14	Lgl Iliaca Communis vänster ICG NEG					
15	Lgl Iliaca Communis vänster ICG POS					
16	Lgl Presacral vänster ICG NEG					
17	Lgl Presacral vänster ICG POS					
18	Lgl Paraaortalt nedom IMA ICG NEG					
19	Lgl Paraaortal nedom IMA ICG POS					
20	Lgl Paraaortal ovan IMA ICG NEG					
21	Lgl Paraaortal ovan IMA ICG POS					
22	SLN Parametrium höger					
23	SLN Parametrium vänster					
24	SLN typ 1 presacral höger					
25	SLN typ 1 presacral vänster					
26	SLN typ 1 iliaca externa höger					
27	SLN typ 1 obturatorius höger					
28	SLN typ 1 iliaca externa vänster					
29	SLN typ 1 iliaca obturatorius vänster					
30	SLN typ 1					
31	SLN typ 1					

32	SLN typ 2					
33	SLN typ 2					
34	SLN makro ICG pos ICG neg					
35	SLN makro ICG pos ICG neg					
36	SLN anatom iliaca externa höger					
37	SLN anatom Iliaca externa vänster					
38	SLN anatom obturatorius höger					
39	SLN anatom obturatorius vänster					
40	SLN anatom communis höger					
41	SLN anatom communis vänster					
42	SLN anatom presacral höger					
42	SLN anatom presacral vänster					

Numbers 30-35 will be used for describing locations outside the most common sites and for SLN type 2 and SLN macro as appropriate. The locations will be written by hand on list and labels for jars.

Histopathologic evaluation of the sentinel nodes and the non-sentinel nodes.

All macroscopically identified SLN lymphoid tissue will be embedded and bisected if the minimum thickness exceeded 3 mm. If no macroscopically lymphoid tissue is identified in SLN or parametrial tissue the most suspicious find will be embedded and microscopically investigated. Ultrastaging using hematoxylin/ Eosin staining will be performed in five sections at three different levels, separated by 200 µm, if the maximum diameter of the SLN tissue exceeds one mm. From first and second level immunohistochemistry (pan-cytokeratin, MNF 116) will be performed. If no macroscopically lymphoid tissue is identified in SLN or parametrial tissue the most suspicious find will be embedded and microscopically investigated. ITC can be detected by Hematoxylin/Eosin or by Immunohistochemistry alone.

Non-SLN will be bisected. Non-SLN less than 3 mm in thickness will be embedded whole, and from nodes thicker than 3 mm at least half the node will be embedded. The slides will be evaluated after hematoxylin/Eosin staining.

Classification of tumor size in SLN's

Sentinel nodes will be classified according to a modification of the AJCC staging for axillary nodes from breast cancer as follows:

Macrometastases = tumor greater than 2.0 mm in diameter.

Micrometastases = tumor cell aggregates between 0.2 and 2.0 mm in diameter.

Isolated tumor cells =individual tumor cells or aggregates that are less than 0.2mm in diameter, usually detected by immunohistochemistry.

Tumor absent – no tumor cells identified in H&E (or immunohistochemically, if applicable) stained sections.

Non-sentinel lymph nodes will be reported as positive or negative for metastases based upon routine sectioning and examination of a single H&E stained section.

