11. STATISTICAL CONSIDERATIONS

This study is designed to evaluate the ability of the sentinel node (SLN) technique to determine pelvic lymph node metastases in patients with low- and high risk endometrial cancer as a replacement for a full lymphadenectomy in the latter and as an increased diagnostic procedure in the former.

The main statistical endpoint will be to evaluate the SLN concept by a non-inferiority analysis, i.e its ability to detect nodal metastatic disease compared with an estimated proportion which with a 50/50% distribution of LREC and HREC result in approximately 12% of women having pelvic nodal metastases. This will be tested against 8% metastatic SLN's as null-hypothesis. With a one-sided analysis (Alfa-error of 5% and 80% power) 362 patients need to be included with a planned interim analysis after 150 patients.

If then 22 or more patients are identified as SLN-node positive the null-hypothesis will be rejected and the study closed. If 12 or fewer patients are identified as SLN node positive the study will be closed for futility. If the number of node positive patients is between 12 and 21 the study will continue to enroll a total of 362 patients (Fleming, 1982).

The measurements of leg volume/lymphedema are based on an estimated risk for lymphedema following SLN only of 1% (null hypothesis) compared with the group of SLN positive (HREC and LREC) with an estimated risk of 4% (20% node positive with 20% risk of lymphedema) with an estimated distribution between group of 88% SLN negative and 12% SLN positive with restaging (SLN+LND). A total of 169 patients need to be included with a planned interim analysis after 65 patients. If 3 or more patients in the SLN+LND group have lymphedema the null hypothesis can be rejected provided no more than one patient in the SLN only group have developed lymphedema.

BIBLIOGRAPHY

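### Women with suspect nodes before surgery (group 3) enter the primary SLN-positive count, so the decision limits mix nodes found by imaging or inspection with nodes found by ICG mapping

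*Combined protocol and SAP*

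**What the plan says.** **Who is enrolled.** Section 3 admits women who are "clinically stage I-II planned for primary surgery". The overview study plan applies the stage limit to the uterine tumour. The overview and Section 4.0/5.0 (Surgical Procedures) both define group 3: "Any endometrial cancer with cancer suspect pelvic or paraaortic nodes", with a short axis of 16 mm or more. The basic-data form (Appendix 1) keeps women with enlarged nodes in the study. Its instruction to exclude applies only to locally advanced or distant disease.

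**How they are treated.** For group 3, Section 4.0/5.0 says "Patient upfront surgery planned for pelvic and paraaortic lymphadenectomy". The next sentence makes lymphadenectomy depend on a positive frozen section.

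**What counts as an SLN.** Under Sentinel Node Identification, macroscopically suspect nodes are SLN macro "regardless of ICG uptake but with information on ICG positivity or not". Section 8 evaluates metastasis detection on types 1-2, macro and anatomy together, and adds a separate evaluation of ICG-defined nodes (types 1-2).

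**What decides the trial.** Section 11 expects the case mix to "result in approximately 12% of women having pelvic nodal metastases", and continues: "This will be tested against 8% metastatic SLN's as null-hypothesis". At the interim after 150 women: "If then 22 or more patients are identified as SLN-node positive the null-hypothesis will be rejected and the study closed". Twelve or fewer positives closes the study for futility. Section 11 has no rule for group 3 and does not use the type 1-2 evaluation.

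**The concern.** Section 11 says SLN is meant to replace full lymphadenectomy in high-risk women. The women who bear most on that question have no visibly suspect nodes. Group 3 women come with a nodal finding on imaging, and a metastatic node that took up no ICG still makes its patient SLN-positive through the macro category.

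The test looks only at the proportion of SLN-positive women. It cannot tell a metastasis found by mapping from one found by imaging or inspection. A small group with high positivity could move the count towards the rejection limit without saying anything about mapping in the rest. At stake are the interim decision, the final conclusion, and the claim about replacing lymphadenectomy.

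**Working it through.** **Inputs from the documents (Sections 9 and 11).** Null 8%, alternative about 12%, one-sided alpha 5%, power 80%, N = 362, interim at n1 = 150, reject at 22 or more, futility at 12 or fewer. I take 13 to 21 as continuing.

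**Inputs not in the documents.** The final cut-off r, the group 3 share g and the group 3 SLN-positive rate q. I infer r. I assume g = 1% to 3% and q = 60%, and vary q.

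**Step 1: reproduce the design.** With X1 ~ Bin(150, p) and X2 ~ Bin(212, p), the chance of rejection is

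P(p) = P(X1 ≥ 22) + Σ over x = 13..21 of P(X1 = x) · P(X2 ≥ r − x).

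With r = 38, P(0.08) = 0.0497 and P(0.12) = 0.801. With the stated interim limits, 362 is the smallest total that meets both targets. This reproduces the plan: "With a one-sided analysis (Alfa-error of 5% and 80% power) 362 patients need to be included".

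**Step 2: the room available.** At 8% the expected count is 0.08 × 362 ≈ 29, about 9 below the cut-off of 38. Group 3 shifts the expected count by 362 × g × (q − 0.08). At g = 3% and q = 60% that is 362 × 0.03 × 0.52 ≈ 5.6.

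**Step 3: two readings of the benchmark.**

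- Reading A: 8% and 12% describe women without suspect nodes, and the rate in those women is exactly 8%. The overall rate is p = (1 − g) × 0.08 + g × q.
- Reading B: 12% already includes women like group 3. The null of 8% then corresponds to finding 8/12, or two-thirds, of metastases. If two-thirds are found in the other women and every group 3 metastasis counts, p = (2/3) × (0.12 − g × q) + g × q. At q = 60% this is 0.08 + 0.2 × g.

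Results at q = 60%:

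| Group 3 share | Women of 362 | p, reading A | P(reject), A | p, reading B | P(reject), B |
|---|---|---|---|---|---|
| 1% | 3.6 | 8.52% | 10.0% | 8.2% | 6.6% |
| 2% | 7.2 | 9.04% | 17.6% | 8.4% | 8.6% |
| 3% | 10.9 | 9.56% | 27.7% | 8.6% | 11.0% |

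Under reading A at a 3% share, q = 30%, 50% or 80% gives 11.8%, 21.6% or 41.5%. At a 1% share and q = 30% it is 6.8%.

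**Step 4: what leaving group 3 out would cost.** Under reading A, alpha and power hold, and 362 women outside group 3 need 362/(1 − g) enrolled: 366, 370 or 374. Under reading B, the true rate in the others is (0.12 − 0.6 × g)/(1 − g) = 11.5%, 11.0% or 10.5%. Power with 362 such women is then about 72%, 62% or 50%.

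**Step 5: what a recount would cost.** Suppose a group 3 woman counted as positive only if a type 1-2 SLN were positive, while staying in the denominator. Under reading B with g = 3%, q = 60% and half of the positives ICG-positive, the detectable rate is 0.12 − 0.03 × 0.30 = 11.1%. Power is about 63%.

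**The case against.** The case for the plan as written has real weight.

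- **Enrolling group 3 is deliberate.** A reader might infer that these women breach eligibility. The documents do not support that: the overview refers to the uterine tumour, the exclusion list does not name enlarged nodes, and the form retains such women. What stands is a wording gap in Section 3.
- **SLN macro belongs to the algorithm under test.** Section 1 evaluates an anatomically based algorithm with its own SLN definition, and Section 8 says openly that all types are pooled. Counting macro nodes is therefore not an error.
- **The women are not irrelevant to replacing lymphadenectomy.** A reader might infer that they have the operation in any case. One sentence for group 3 reads that way, but the next makes it conditional on frozen section.
- **Inflation is not shown.** Section 2 wants consecutive, representative patients, and 8% and 12% may be rates for all of them. An overall rate of 9.6% is then not the null. Against this, Section 1 builds the benchmark from uterine histology with no nodal-imaging term, and reading B still gives more than 5%. The source population is not stated, so neither reading can be ruled out.
- **The figures are upper readings of the imaging effect.** They count every group 3 positive, including women whose type 1-2 SLN is also positive. If half of them are (reading A, 3% share, 60% positive), a count limited to type 1-2 in group 3 gives 11.8% rather than 27.7%. Suspect paraaortic nodes alone do not make a pelvic SLN positive, and nothing says that every 16 mm imaging finding becomes SLN macro.

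**Conclusion.** The point holds in a conditional form. Group 3 women enter the count behind the 12/22 limits and the final test. Their macroscopically suspect nodes count without ICG uptake, and the type 1-2 evaluation that would separate the two sources of positivity decides nothing.

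The documents do not support a flat statement that the result is inflated. The size depends on three things that they do not give: whom the 8% and 12% describe, the share and positivity of group 3, and the final cut-off (38 is inferred). At 60% positivity and shares of 1% to 3%, the chance of rejection is about 10% to 28% if the benchmarks exclude such women. It is about 7% to 11% if the 12% includes them and mapping finds two-thirds of metastases in the others. The nominal figure is 5%.

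The plan should address this, because a handful of women can affect the decision and the data needed to show it are already collected.

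**What to change.** 1. **Section 11, analysis.** Keep the pooled count as the primary analysis. Pre-specify, at interim and final, the same result without group 3 and for ICG-defined SLN (types 1-2) only. Limit the conclusion about replacing lymphadenectomy to what holds without group 3.
2. **Section 11, benchmark.** State whether the 8% and 12% figures include women with suspect nodes.
3. **Section 3, the overview and Section 4.0/5.0.** Reconcile the stage wording of the inclusion criteria with that of the overview and with group 3. Reconcile the two lymphadenectomy sentences for group 3, one planning it upfront and one making it depend on frozen section. Which of them applies is for the investigators to settle.

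Do not recode group 3 women with a positive SLN macro as SLN-negative in the primary count. That would score proven metastases as missed and treat macro nodes differently in groups 1 and 2. It would also cost power if the 12% includes such women (step 5).

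**Cost.** Wording and a little more analysis. Enlarged nodes, planned-surgery group, SLN type and ICG status are already on the forms. The analysis without group 3 has lower power if the 12% includes these women (step 4), so it should be read as a check on the primary result and not as a second hurdle.
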